9.3 Pregnancy

All study participants are required to be using an effective method of contraception at enrollment, and intending to use the same method for the duration of study participation. Study staff will provide contraceptive counseling to enrolled participants as needed throughout the duration of study participation and will facilitate access to contraceptive services through direct service delivery and/or active referrals to local service providers. Study staff also will provide participants with male condoms and will counsel participants to ideally use these condoms during every sex act throughout study participation.

Pregnancy testing will be performed at the Screening, Enrollment, and 16-Week/Study Termination study visits, and when clinically indicated during study follow-up. Participants will be encouraged to report all signs or symptoms of pregnancy to study staff during the course of the study. The site IoR or designee will counsel any participants who become pregnant regarding possible risks of study IVR use according to site-specific SOPs. The IoR or designee also will refer the participant to all applicable services; however, sites will not be responsible for paying for pregnancy-related care. Participants who are pregnant at the 16-Week/Study Termination visit will continue to be followed until the pregnancy outcome is ascertained (or, in consultation with the PSRT, it is determined that the pregnancy outcome cannot be ascertained). Study staff will be

responsible for follow-up with the participant until the pregnancy outcome is determined. Pregnancy outcomes will be reported on relevant case report forms.

Participants who become pregnant during the course of the study will permanently discontinue study product use but will not routinely be withdrawn from the study. Rather, if the participant does not withdraw her consent, every effort will be made to complete all study visits. All protocol-specified procedures will continue except:

- Provision of study IVR (for participants randomized to the IVR arm)
- Pelvic exam including colposcopy (unless clinically indicated)

9.4 Criteria for Temporary or Permanent Discontinuation of Study Product

Participants may voluntarily discontinue product use for any reason at any time. Site IoRs will temporarily or permanently discontinue participants from product use per the specifications below, which may be further clarified in the SSP. Site IoRs also may, with the approval of the PSRT, temporarily or permanently discontinue participants from study IVR use for reasons not shown here or in the SSP, e.g., to protect their safety.

The criteria for temporary discontinuation of study IVR use for an individual participant are outlined in Section 9.2.

The criteria for permanent discontinuation of further study IVR use for an individual participant are outlined in Section 9.2, but also include:

- Pregnancy
- HIV-1 seroconversion
- Completion of regimen as defined in the protocol
- Request by participant to terminate treatment
- Clinical reasons as determined by the study clinician

Participants who temporarily or permanently discontinue product use will continue to complete study visits and procedures as originally scheduled (except that study IVRs will no longer be provided during the time the participant will not be using the study IVR).

9.5 Criteria for Early Termination of Study Participation

Participants may voluntarily withdraw from the study for any reason at any time. Site IoRs may, with the approval of the PSRT, withdraw participants before their scheduled termination visit to protect their safety. Participants also may be withdrawn if the study sponsors, government or regulatory authorities (including the Office for Human Research Protections (OHRP)), or site IRBs/ECs terminate the study prior to its planned end date. Site investigators are required to consult the Protocol Chair and Protocol Biostatistician prior to the site-initiated withdrawal of any study participant. Study staff will record the reason(s) for all withdrawals in participants' study records. In the event

that participants who voluntarily withdraw from the study wish to re-join the study, they may resume study procedures and follow-up, provided the participant is still within her original 16-week follow-up period.

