	Pelvic Samples	
 • Gram stained smear of vaginal fluid, obtained from lateral vaginal wall • Vaginal swabs for vaginal flora assessments • Vaginal fluid tested for Trichomonas vaginalis by rapid test (CLIA waived test)* † • Vaginal pH* † • Vaginal fluid for wet mount microscopy (KOH for vulvovaginal candidiasis)* † • Vaginal fluid for wet mount microscopy (saline for BV)* † • Herpes culture †* • Cervical swab for NAAT for GC/CT* • US sites only: a biofilm assessment will be performed on the used ring that is removed at the 12-Week Visit if the ring is removed by a study clinician. 
 ○ In the event that an IVR is removed at an earlier visit, the used ring will have a biofilm assessment if assessment criteria are met, including IVR removal by a study clinician/designee.
Study Product Supply		
 • Provide study specified male condoms • Study clinician/designee to remove used study IVR at 12-Week Visit • Provide study IVR at 4-and 8-Week Visits in case of ring removal/expulsion* • Collect used study IVR at 4-and 8-Week Visits in case of ring removal/expulsion* 
 ○ In case of ring expulsion or removal, participants may also receive a bottle of water with which to rinse the study ring (4- and 8-Week Visits only)

*If clinically indicated

† Per local standards/guidelines

7.4 16-Week/Study Termination Visit

Table 7: 16-Week/Study Termination Visit

16-Week/Study Termination Visit	
Component	Procedures
Administrative and Regulatory	
 • Review/update locator information • Provide available test results • Provide reimbursement for visit • Schedule next study visit, if applicable
Behavioral	
 • Administer final behavioral assessment (in the event that a participant drops out of the study prior to the 16-Week Visit, the final behavioral assessment will not be administered) • Provide counseling 
 ○ Contraceptive ○ HIV testing process ○ HIV/STI risk reduction/male condom • Administer final acceptability assessment (for Group A in the event that use of the study IVR is permanently discontinued at an earlier visit)*

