7.5 Follow up Procedures for Participants who Discontinue Study Product

Participants who discontinue study product will be encouraged to remain in the study if they are willing, for safety evaluations according to the study follow up schedule with the exceptions described below.

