8.3 Adverse Events Definitions and Reporting Requirements

8.3.1 Adverse Events

An AE is defined as any untoward medical occurrence in a clinical research participant enrolled in a clinical trial and which does not necessarily have a causal relationship with an investigational product or study participation. As such, an AE can be an unfavorable or unintended sign (including an abnormal laboratory finding, for example), symptom or disease temporally associated with the use of an investigational product or study participation, whether or not considered related to the product or study participation. This definition will be applied beginning at the time of random assignment. The term “investigational product” for this study refers to the study IVR.

Study participants will be instructed to contact the study site staff to report any AEs they may experience. In the case of a life-threatening event, participants will be instructed to seek immediate emergency care. Where feasible and medically appropriate, participants will be encouraged to seek medical care where the study clinician is based, and to request that the clinician be contacted upon their arrival. With appropriate permission of the participant, whenever possible, records from all non-study medical providers related to AEs will be obtained and required data elements will be recorded on study case report forms. All participants reporting an AE (including pelvic exam abnormalities, excluding colposcopic findings) will be followed clinically until the AE resolves (returns to baseline) or stabilizes.

Study site staff will report on study case report forms all AEs, excluding findings observed by colposcopy only, reported by or observed in enrolled study participants from the time of enrollment (random assignment) until study termination, regardless of severity and presumed relationship to study product. The DAIDS AE Grading Table Version 1.0, Dec 2004 (clarification dated August 2009), Addendum 1 (Female Genital Grading Table for Use in Microbicide Studies), will be the primary tool for grading AEs for this protocol, except that asymptomatic BV will not be a reportable AE. AEs not included in the Female Genital Table for Use in Microbicide Studies will be graded by

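### Table 7 bars the final behavioural assessment for early leavers, and Sections 9.4 and 9.5 attach different follow-up to the same safety ground without saying which applies

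*Protocol*

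**What the plan says.** **Behavioural assessment.** The behavioural row of Table 7 (Section 7.4) carries a parenthesis: "in the event that a participant drops out of the study prior to the 16-Week Visit, the final behavioral assessment will not be administered". Appendix I marks the behavioural assessment at Enrollment and Weeks 4, 8, 12 and 16 and leaves the interim column blank. Section 7.6 allows other procedures at interim visits as indicated, but names no behavioural assessment. The same table does provide a catch-up final acceptability assessment at Week 16 for ring-arm women who stopped the ring earlier. Sections 3.2 and 10.2.2 make change in sexual behaviour and vaginal hygiene a secondary objective, over 12 weeks, and a secondary endpoint. Section 10.8.3 compares the arms by GEE on the longitudinal measures and names Week 16 as a collection point.

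**Stopping the ring or leaving the study.** Section 9.4 lets the site investigator, with PSRT approval, "temporarily or permanently discontinue participants from study IVR use for reasons not shown here or in the SSP, e.g., to protect their safety". It then says: "Participants who temporarily or permanently discontinue product use will continue to complete study visits and procedures as originally scheduled". Section 9.5 adds: "Site IoRs may, with the approval of the PSRT, withdraw participants before their scheduled termination visit to protect their safety". Two safeguards follow there: "Site investigators are required to consult the Protocol Chair and Protocol Biostatistician prior to the site-initiated withdrawal of any study participant" and "Study staff will record the reason(s) for all withdrawals in participants' study records". Section 8.3.1 has adverse events reported on case report forms from randomization "until study termination, regardless of severity and presumed relationship to study product".

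**The concern.** The Table 7 clause is an instruction, not an acknowledgement that some women cannot be reached. It applies equally to a woman who is willing to answer on her way out. Women who leave early may do so for reasons connected with sexual behaviour or with the ring, so the unasked answers need not resemble those of women who stay. An unweighted GEE comparison relies on missing visits being unrelated to the outcome, and here some of the missingness is created by the plan.

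The second matter is one of clarity. The same ground (the woman's safety) and the same approver (the PSRT) lead under 9.4 to continued follow-up and under 9.5 to its end. Section 9.5 does not say when one applies rather than the other, nor whether adverse event reporting goes on for a woman withdrawn this way. The primary safety endpoint counts events during follow-up, so the plan should settle this.

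**Working it through.** **1. Who is affected by the Table 7 clause.** Taking Table 6, Table 7 and Appendix I together:

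| Woman leaves | Behavioural data held | What the clause forgoes if she attends an exit visit |
|---|---|---|
| before Week 4 | Enrollment only | her only follow-up measurement |
| between Weeks 4 and 8 | Enrollment, Week 4 | the interval since Week 4 |
| between Weeks 8 and 12 | Enrollment, Weeks 4, 8 | the interval since Week 8 |
| between Weeks 12 and 16 | Enrollment, Weeks 4, 8, 12 | the interval since Week 12, after the 12-week objective window |
| at a scheduled visit (4, 8 or 12) | up to and including that visit | nothing before her exit |

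The loss per woman is at most one measurement. It matters most in the first row, where without it no change from baseline exists, and least in the fourth.

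**2. How many.** Inputs: 252 women, 168 and 84 by arm (Section 10.1); 95% retention target over 16 weeks (Section 10.7).
- All leavers: 0.05 × 252 = 12.6, about 13.
- If losses follow the allocation: 0.05 × 168 = 8.4 on the ring and 0.05 × 84 = 4.2 without it.

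This is a ceiling at the target. It includes women lost to contact, whom no rule could assess, and women who leave at a scheduled visit. The protocol does not split the 5% by reason.

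**3. Whether a design figure is disturbed.** Section 10.4.1 gives 80% power for an upper limit of 6.9% at 5% against 5%, with 168 and 84 women. Enumerating both binomials with a one-sided 95% Wald limit, p1 − p0 + 1.645 × √[p1(1−p1)/168 + p0(1−p0)/84] ≤ 0.069, gives 80.7%, so the figure is reproduced approximately. With 5% loss in each arm (160 and 80) the same enumeration gives 78.6%. That change is ordinary attrition and is not caused by either clause.

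**4. Sections 9.4 and 9.5 side by side.**

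| | 9.4 | 9.5 |
|---|---|---|
| Ground | her safety (given as an example) | her safety |
| Approval | PSRT | PSRT, plus consultation of Protocol Chair and Protocol Biostatistician |
| What stops | ring use | study participation |
| Visits afterwards | continue as scheduled | not stated; participation has ended |
| Adverse event reporting | continues to study termination | not stated; on a natural reading it ends with her participation |

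The sections do not contradict each other outright, since one governs product and the other participation. What is missing is the dividing line when the concern is about the ring.

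**The case against.** **On Table 7.** Behaviour is measured at Enrollment and Weeks 4, 8 and 12, the objective covers 12 weeks, Week 16 falls after ring removal, and the GEE uses every visit a woman attended. The protocol schedules no exit visit, and many leavers will not attend one. All of this stands and is why the point is small. It does not justify forbidding the assessment when a leaver is present and willing.

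**On 9.5.** Retention is the protocol's default. Section 7.5 says "Participants who discontinue study product will be encouraged to remain in the study if they are willing", and Sections 7.5.3 and 9.3 likewise continue procedures. Participation has risks of its own in both arms (examinations, phlebotomy, loss of confidentiality, social harms), so withdrawal need not concern the ring. The route requires PSRT approval, consultation of the biostatistician and a recorded reason. This too stands.

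**Stronger readings that a reader might infer.** One is that these rules discard outcome data. They do not: Section 10.8.2 includes data from all visits in the ITT safety analysis, and a woman withdrawn after a Grade 2 event is already counted. Nor is a woman with an open event dropped, because Section 8.3.1 has it followed clinically until it resolves or stabilizes and Section 7.13 allows a final contact. Another is that withdrawals will fall on the ring arm and pull the safety bound toward a favourable result. With 4 events in 84, a score-type one-sided 95% upper bound is 4.4 points at 8 ring events in 168, 3.7 at 7 and 2.9 at 6. This shows only what a lost event would do, on a bound other than the exact one specified. The protocol gives no number or arm for site-initiated withdrawals and no ground for assuming that any event would be lost.

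**Conclusion.** The concern holds as a minor improvement. The Table 7 clause forgoes at most one secondary-endpoint measurement per woman, for fewer than about 13 women if the 95% retention target is met. Women leaving before Week 4 are the ones for whom it would matter most. That the loss is informative is plausible but not shown. Neither primary endpoint is affected by this clause, and nothing here makes a power or sample-size figure wrong.

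The 9.4 and 9.5 wording is a smaller, separate point of reconciliation. Neither the size nor the direction of any effect on the safety bound can be derived from the protocol.

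**What to change.** 1. Delete the parenthesis in the behavioural row of Table 7, and state that the behavioural assessment is offered at the last visit a departing woman agrees to attend. Add the matching entry to the interim column of Appendix I. Cost: wording, plus one ACASI session for at most about a dozen women, fewer in practice because some will be lost to contact.

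2. Reconcile Sections 9.4 and 9.5 by cross-reference, and state whether scheduled visits and adverse event reporting continue, with the woman's consent, when the safety concern is about the ring. When a woman should be withdrawn, and which examinations she should then have, is a clinical decision for the protocol team. Cost: a sentence or two in 9.5, with no change to sample size or analysis.

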10 STATISTICAL CONSIDERATIONS

10.1 Overview and General Design

This is a multi-site, open-label, two-arm, 2:1 randomized, controlled trial comparing the expanded safety of, and adherence to, a study IVR for 12 weeks of use to no IVR use among sexually active, HIV-uninfected women. A total of 252 women (168 and 84 in the IVR and no IVR arms, respectively) will be randomized, 150 in Pune, India (100 and 50 in the IVR and no IVR arms, respectively) and 102 (68 and 34 in the IVR and no IVR arms, respectively) for the two combined US sites (with competitive enrollment for the two US sites).

10.2 Study Primary and Secondary Endpoints

10.2.1 Study Primary Endpoints

Consistent with the primary study objectives to assess the safety and adherence of the study IVR when used for 12 consecutive weeks, the following primary endpoints will be assessed:

Safety

- Evidence of Grade 2 or higher genitourinary events as defined by the DAIDS Table for Grading the Severity of Adult and Pediatric Adverse Events, Version 1.0, Dec 2004 (Clarification dated August 2009), Addendum 1 (Female Genital Grading Table for Use in Microbicide Studies)

Adherence

- For women randomized to the study IVR arm, participant report of frequency of study IVR removal (voluntary and involuntary) and duration without IVR inserted in vagina over 12 weeks of use

10.2.2 Study Secondary Endpoints

Consistent with the secondary study objectives to describe the changes in sexual behavior and changes in vaginal hygiene practices, to evaluate the acceptability of the study IVR, and to measure vaginal flora characteristics, and changes of these over the course of study IVR use, the following endpoints will be assessed:

- Per participant report, changes in sexual behavior and vaginal hygiene practices
- For women randomized to the study IVR arm, participant report of acceptability including genitourinary discomfort, ring insertion/removal issues, expulsions (including context of expulsion), and changes in participant and partner sexual feeling
- Changes in vaginal flora from enrollment to week 12 as measured by Gram stain Nugent score and quantitative culture (Note that these quantitative vaginal cultures will only be available from the US sites, therefore reducing the available sample size for this objective)

10.2.3 Exploratory Endpoint

- Changes in vaginal biomarkers (US sites only)
- Presence of biofilms on study IVR surface (US sites only)

10.3 Study Hypotheses

MTN-005 hypothesizes that the study IVR will be safe and will be used as directed by US and non-US women over 12 weeks of use.

10.4 Sample Size

10.4.1 Safety Endpoints

The proposed total sample size is N=252 randomized into 2 arms: 168 and 84 women in the study IVR and no IVR arms, respectively. Given that assessing adherence to the study IVR is a primary objective, and that this can only be assessed in the study IVR arm, a 2:1 randomization was selected to increase the precision on estimates of adherence and acceptability. A 2:1 randomization will slightly decrease the power for the comparison of safety profiles between the study IVR and no IVR arms, but the decrease in power is not substantial. Participants who are non-adherent to the study product and/or the study visit schedule will not be replaced.

For the study IVR arm, if the true rate of a given toxicity endpoint is 5%, 168 women provide 80% power to exclude safety and toxicity endpoint rates greater than 10.0%, where the safety and toxicity endpoints for a woman are defined as the occurrence of the safety endpoint during follow-up, that is the occurrence during follow-up of evidence of Grade 2 or higher genitourinary events as defined by the DAIDS AE Grading Table, Version 1.0, Dec 2004 (clarification dated August 2009), Addendum 1 (Female Genital Grading Table for Use in Microbicide Studies).

For the no IVR arm, if the true rate of a given safety and toxicity endpoint is 5%, 84 women provide 80% power to exclude safety and toxicity endpoint rates greater than 13.3%.

The safety and toxicity rates of women using the study IVR and the rates for those not using the study IVR will be formally compared. A sample size of 252 women with a 2:1 randomization (i.e. 2 IVR : 1 no IVR) will assure with 80% power that a 95% confidence interval for the difference between the study IVR and no IVR safety and toxicity rates has an upper limit no more than 6.9% when the true toxicity rates for study IVR and no IVR are both 5%. The above calculations have been performed assuming true rates of toxicity of 5%. However, it is anticipated that the true rates are smaller than 5%. If this is the case, the above power computations are conservative and the actual power will be slightly higher. Table 8 displays 95% confidence interval upper bounds for different assumptions on the safety and toxicity rates in the IVR and no IVR arms. These bounds correspond to non-inferiority bounds computed using an exact one-sided 95% confidence interval for the difference in rates between the two arms as described in the Primary Safety Analysis.

Table 8: Confidence Interval for Upper Bound for the Difference Between IVR and no IVR Safety and Toxicity Rates

		Assumed rate in IVR arm					
Assumed rate in no IVR arm		1%	5%	7.5%	10.0%	12.5%	15.0%
1%		3.6%	9.8%	13.0%	-	-	-
5%		-	6.9%	10.1%	13.1%	-	-
7.5%		-	-	8.1%	11.3%	14.2%	-
10.0%		-	-	-	9.4%	12.3%	15.2%
12.5%		-	-	-	-	10.4%	13.2%
15.0%		-	-	-	-	-	11.2%

10.4.2 Adherence Endpoints

Adherence will be measured by the percentage of women who keep the IVR inserted in the vagina over the course of 12 weeks. Adherence can only be assessed among the 168 women randomized to the study IVR arm. A sample size of 168 women will provide a precision of 6.4% (i.e. half-width of the 95% exact confidence interval) assuming an observed adherence of 80%. Substantial heterogeneities in adherence between the Indian and the US sites might be observed in which case adherence will be estimated separately for Indian and US women. For the Indian site, a sample size of 100 women using the study IVR will provide a precision of 8.3% assuming an observed adherence of 80% while this precision would be 10.2% with a sample size of 68 US women using the study IVR.

10.4.3 Acceptability Endpoints

Several components of acceptability (e.g., report of discomfort, removal and insertion difficulties, episode of expulsions, bowel, urinary and sexual difficulties (see Section

7.8)) will be used to assess overall acceptability. Each component will be assessed by a dichotomous measure where women will be categorized into (1) those reporting no acceptability issues during the 12 weeks of study IVR use (e.g., those reporting no discomfort) and (2) those reporting at least one issue during the 12 weeks of study IVR use (e.g., those reporting some discomfort). Acceptability can only be assessed among the 168 women randomized to the study IVR arm. An acceptability endpoint is defined as a negative report by a participant, on any of the above components of acceptability. A sample size of 168 women will provide a precision of 6.4% (i.e. half-width of the 95% exact confidence interval) assuming an observed acceptability of 80%. Substantial heterogeneities in acceptability between the Indian and the US sites might be observed in which case acceptability will be estimated separately for Indian and US women. For the Indian site, a sample size of 100 women using the study IVR will provide a precision of 8.3% assuming an observed acceptability of 80% while this precision would be 10.2% with a sample size of 68 US women using the study IVR. Due to the smaller sample size within each site, no formal comparison will be performed for comparing adherence and acceptability between sites.

